9.1. HBV-specific Self-stigma PRO Scale

9.1.1. Definition

The HBV-specific self-stigma scale is a hepatitis B-specific PRO instrument designed to assess the experience and impact of self-stigma. The current version consists of 37 items. The items cover aspects of self-stigma such as a) devaluation, inferiority, and worthlessness, b) marginalization and alienation, c) secrecy and concealment, d) shame and guilt, and e) withdrawal and social isolation. Each of the 37 items is graded on a 5-point Likert scale (1="Never", 2="Rarely", 3="Sometimes", 4="Often", and 5="Always").

9.1.2. Analysis Methods

Descriptive statistics of the actual values and change from baseline values at each timepoint (including baseline and available analysis time point) for the scores will be displayed for each aspect by intervention arm. The proportion of participants experiencing a clinically important improvement or worsening from baseline (if applicable) at each timepoint will be calculated by intervention arm. Analyses will also be performed on the changes from baseline at specific time points as appropriate for different subgroups: participants with versus participants without HBsAg seroclearance 24 weeks and 48 weeks after completion of all study intervention at Week 48.

In addition, effect sizes will be calculated to measure the magnitude of difference between means in all different intervention arms using an ANCOVA, with intervention arm, and 3 randomization stratification factors, as main effect in the model, and the three 2-way intervention arm-stratification factor interaction terms, and baseline as covariate. The LS means of the change from baseline on the analysis time points with estimates, SE, 90% CI, p-values will be presented. A graphical representation may be used to display the adjusted mean change from baseline.

9.2. 5-Level EuroQol 5-Dimension Questionnaire

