9.2. Sample Size Determination

The total study sample size is 120 participants who will be randomly assigned to one of the two intervention arms in a 2:1 ratio (JNJ-3989+JNJ-6379+NA: placebo+placebo+NA). Statistical power to test the primary hypothesis was assessed using the Mantel-Haenszel test with a 1-sided Type 1 error rate of 0.05, assuming the observed percentage of participants with HBsAg seroclearance at Week 72 in the placebo+placebo+NA arm to be 5%. The sample size of 80 participants in the investigational arm and 40 participants in the control arm provides >91% statistical power to detect a $\geq 20\%$ difference in the primary endpoint.

The 2:1 randomization ratio (N 80:40, JNJ-3989+JNJ-6379+NA:placebo+placebo+NA) was chosen to balance statistical and clinical considerations as it provides adequate evidence of efficacy and safety, with the benefit of offering study participants a higher chance to receive investigational treatment. Safety will be compared between arms descriptively only, and no inferential testing is planned.

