5.4.2.2.1. Fibrosis

The changes from baseline at end of study intervention and follow-up will be summarized using descriptive statistics (for example, may include n, mean, SD, 90% CI, median, minimum, maximum) by intervention arm. The comparison between intervention arms will be done using ANCOVA with intervention arm, randomization stratification factors as main effects in the model and baseline score as covariate.

At each assessment time point, a frequency distribution of severity scores will be produced by intervention arm. A graphical display will also illustrate the findings.

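### The self-stigma ANCOVA includes three arm-by-stratum interactions but states no LS-mean weights; under the usual equal weights the arm difference loses precision when strata are uneven

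*SAP*

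**What the plan says.** SAP 9.1.2 states the purpose of the model: "effect sizes will be calculated to measure the magnitude of difference between means in all different intervention arms using an ANCOVA". Its terms are arm, the three randomization factors (screening HBsAg level, race, type of NA), "and the three 2-way intervention arm-stratification factor interaction terms, and baseline as covariate". The output comes from that same model: "The LS means of the change from baseline on the analysis time points with estimates, SE, 90% CI, p-values will be presented". The section does not say how the LS means are weighted over the factor levels, and it plans no separate model without interactions. The rest of 9.1.2 is descriptive, so this is the only modelled comparison of the arms on self-stigma.

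Elsewhere the SAP keeps such interactions out of the main estimate. The fibrosis comparison (SAP 5.4.2.2.1) is an "ANCOVA with intervention arm, randomization stratification factors as main effects in the model and baseline score as covariate". For the primary endpoint, the main estimator (SAP 5.2.2.1.1) is a stratified Mantel-Haenszel difference. Arm-by-factor terms enter only in a sensitivity model used if heterogeneity is found (5.2.2.2.1) and in subgroup work (5.2.4).

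**The concern.** In an ANCOVA without interactions, the difference between two arms' LS means is the arm coefficient and does not depend on the LS-mean weights. Once arm-by-factor interactions are included, the fitted arm effect varies with the factor levels, and the difference depends on how those levels are averaged. Standard LS means give each level of a two-level factor a weight of one half. A level holding 20% of participants (about 8 of 40 controls) then counts as much as the level holding 80%.

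Two things follow. The estimate targets a population split evenly on all three factors rather than the one enrolled. Its SE also grows with the imbalance, because the thin levels are given extra weight. What is at stake is the width of the reported CI, and which population the effect size refers to, for an exploratory patient-reported outcome.

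**Working it through.** **Inputs.** The planned size is "The sample size of 80 participants in the investigational arm and 40 participants in the control arm" (Protocol 9.2). PRO analyses use the ITT set (SAP 9), so at most 120 participants. Allocation uses permuted blocks stratified by the three two-level factors (Protocol 6.3). Two inputs are assumed: the factor splits, which neither document gives, and equal LS-mean weights, which are the usual definition.

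**The plan's own figure.** No SE or power is given for the PRO model. The sample-size statement was checked to confirm the design inputs. For 25% v 5%, 80 v 40, one-sided 0.05:
- pooled rate = 22/120 = 0.183
- null SE = sqrt(0.183 x 0.817 x 0.0375) = 0.0749
- alternative SE = sqrt(0.05 x 0.95/40 + 0.25 x 0.75/80) = 0.0594
- z = (0.20 - 1.645 x 0.0749)/0.0594 = 1.29, so power is about 90.2%

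Exact binomial power of the unstratified Mantel-Haenszel test is 91.7%, which agrees with the stated figure of more than 91%.

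**Closed form.** Take independent factors, balanced across arms, with proportion p_j at one level, and let s be the residual SD.
- Main-effects arm difference: variance V = s^2 (1/80 + 1/40), so SE = 0.194 s.
- Interaction model, equal weights: the contrast is the arm effect at the observed mix plus the sum of g_j (0.5 - p_j), where g_j is the j-th interaction with variance V / [p_j(1 - p_j)].
- SE ratio = sqrt(1 + sum of (p_j - 0.5)^2 / [p_j(1 - p_j)]).

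Each factor's term is 0 at 50/50, 0.01/0.24 = 0.0417 at 60/40, 0.04/0.21 = 0.1905 at 70/30, and 0.09/0.16 = 0.5625 at 80/20.

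**Simulation.** Design matrices were built with N = 120, 2:1 in blocks of 6 within the 8 strata, a baseline covariate, and 1,000 draws per setting.

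| Splits on the three factors | Closed form | SE increase | Simulated (uncorrelated factors) |
|---|---|---|---|
| 50/50 on all | sqrt(1) | 0% | 1.4% |
| 60/40 on all | sqrt(1.125) | 6.1% | 7.8% |
| 70/30 on all | sqrt(1.571) | 25.4% | 28.4% |
| 80/20, 70/30, 70/30 | sqrt(1.943) | 39.4% | 44.0% |

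A repeat run gave ratios of about 1.01, 1.08, 1.29 and 1.45. With latent correlation between the factors of 0.3 or -0.2, the 70/30 row becomes 21.9% or 35.1%, and the last row 35.9% or 51.6%.

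**What this means for the CI.** The simulated main-effects SE is 0.195 s, so the 90% half-width is 1.645 x 0.195 = 0.32 s. At 70/30 it is 0.32 x 1.284 = 0.41 s, and at 80/70/70 it is 0.32 x 1.44 = 0.46 s. In effective sample size, 70/30 corresponds to 120/1.571 = 76 participants (closed form) or 120/1.284^2 = 73 (simulated).

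**Observed-margin weights.** With the interactions kept and the levels weighted by their observed frequencies, the SE exceeds the main-effects SE by only about 0.1%.

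**Per-arm LS means.** Removing the interactions frees the difference from the weights, but not each arm's own LS mean. For Arm 1 in the main-effects model, the equal-weight to observed-margin SE ratio is sqrt(1 + (80/120) x 0.571) = 1.18 at 70/30 and sqrt(1 + (80/120) x 0.943) = 1.28 at 80/70/70. Simulated values are about 1.20 and 1.30.

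**The case against.** The strongest reply is that the loss depends on a setting the SAP does not state. With observed margins the planned model costs almost nothing, so a reader who infers that the SAP prescribes an effect for a 50:50 population goes further than its text. This stands. What the text supports is that both the target and the precision hang on an unstated choice whose usual default is the unfavorable one.

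A reader might also infer a definite loss approaching half the SE. The documents do not support that, since they give no splits and near 50/50 the loss is about 1%. Simulating without blocking gives variance ratios of 1.72 at 70/30 and 2.19 at 80/70/70 (SE x1.31 and x1.48). That overstates the loss for a trial blocked on these same factors.

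Equal weighting is also a legitimate target, and it differs from the enrolled-population effect only if real arm-by-stratum interactions exist. Nothing here shows that they do, so bias is not established. The SAP does use interactions elsewhere: in the models of 5.2.2.2.1 and 5.2.4, and arm-by-baseline in the repeated-measures model of 5.3.2.2.1. The first two are sensitivity or subgroup models, not the main estimate of an arm difference.

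Finally, materiality is low. Self-stigma is exploratory, Protocol 9.4.1.4 calls for descriptive PRO analysis, the scale is still being validated (Protocol 8.1.2), exploratory comparisons carry no multiplicity adjustment (SAP 5.4.2), and by-arm descriptive statistics are reported at every time point. All of this is correct. It limits the importance of the point but does not remove an avoidable loss of precision in the one planned modelled comparison.

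**Conclusion.** The point holds as a minor one. The planned model, read with the usual equal-weight LS means, gives an arm difference that is never appreciably more precise than the main-effects estimate and is less precise when strata are uneven. The loss ranges from negligible at even splits to between a quarter and just under a half of the SE at 70/30 to 80/70/70 with uncorrelated factors. This rests on two assumptions outside the documents, the LS-mean weights and the splits, and the size moves with both. No conclusion about the primary endpoint, the sample size or any decision rule is affected.

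**What to change.** In SAP 9.1.2:
- Take the arm difference, effect size, 90% CI and p-value from an ANCOVA with arm, the three stratification factors and the baseline score, matching SAP 5.4.2.2.1.
- State that per-arm LS means use observed-margin weights. Deleting the interactions alone would leave those means evaluated at even factor levels.
- Fit the three arm-by-factor interactions in a separate model, labelled exploratory.

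If the sponsor prefers to keep a single interaction model, stating observed-margin weights for it recovers nearly all the precision. The cost is a few words in the SAP and one additional model run. No data collection changes, and the interaction information is kept.

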9.2.1. Definition

The EQ-5D-5L questionnaire is a generic health-related quality-of-life assessment that evaluates a participant's self-rated health state on 5 dimensions (mobility, self-care, usual activities, pain/discomfort, anxiety/depression). Additionally, a VAS records the participant's self-rated health on a vertical VAS where the endpoints are labelled 'best imaginable health state' (100) and 'worst imaginable health state' (0).

The EQ-5D-5L questionnaire will be analyzed in 3 ways:

- EQ-5D descriptive system scores (5 scores reflecting each of the 5 dimensions see [Attachment 3](#) for a representative example of the EQ-5D-5L).

An assessment that evaluates a subject's self-rated health state on 5 dimensions (mobility, self-care, usual activities, pain/discomfort, anxiety/depression) with 5 possible levels (no problems (level code = 1), slight problems (level code = 2), moderate problems (level code = 3), severe problems (level code = 4), extreme problems (level code = 5)).

- EQ-5D VAS a continuous score ranging from 0 to 100 (with a possible range from 0 [worst imaginable health] to 100 [best imaginable health]);
This information can be used as a quantitative measure of health outcome as judged by the subject.
- EQ-5D Valuation Index The information of the 5 dimensions of the descriptive system summarized into one index. (a weighted scoring of the 5 dimensions scores with a possible range from 0 to 1);

EQ-5D Valuation index summarizes the information of the 5 dimensions of the descriptive system as below.

- Assign the level code 1, 2, 3, 4 and 5 to each level of the 5 dimensions (see above)
- Create a health state for each patient-time point combination. A health state is a combination of 5 level codes; one level code for each dimension. The dimensions are ordered as described in the attachment.

E.g. health state 12543 indicates ‘no problems in walking about, slight problems washing or dressing myself, unable to do my usual activities, severe pain or discomfort, moderately anxious or depressed’.

- Assign an index value (valuation index) to each observed health state using the UK crosswalk value set as defined in [Attachment 3](#). Based on the origin of the subjects, another method can be used.

Missing Data:

- If – for a questionnaire – one (or more) dimensions of the descriptive system are missing, then
 - The EQ-5D VAS will be tabulated if not missing
 - The valuation index will not be tabulated
 - The non-missing dimensions of EQ-5D descriptive system will be summarized
- If – for a questionnaire – the EQ-5D VAS is missing then the EQ-5D descriptive system and validation index will be tabulated if complete.

9.2.2. Analysis Methods

For the EQ-5D descriptive system, descriptive statistics on the actual value and change from baseline will be presented.

For the EQ-5D VAS and for the Valuation index, descriptive statistics for the actual and change from baseline values at each time point will be displayed. In addition, mean changes from baseline will be explored per subgroup: participants with versus participants without HBsAg seroclearance 24 weeks and 48 weeks after completion of all study intervention at Week 48. The clinically

important thresholds of 7 and 10 will be used to interpret the mean change from baseline in the VAS.

The number (and percentage) of participants with clinically important improvement/ worsening will be presented for EQ-5D VAS:

- Clinical Important Improvement = change from baseline ≥ 7 , and also for ≥ 10
- Clinical Important Worsening = change from baseline ≤ -7 , and also for ≤ -10 .
- Other changes from baseline values are categorized as ‘No Clinically Important Change’.

A cumulative distribution function of the EQ-5D VAS will be drawn at different time points (baseline and changes from baseline).

REFERENCES

Bourne, C. R., Finn, M. G., & Zlotnick, A. (2006). Global structural changes in hepatitis B virus capsids induced by the assembly effector HAP1. *Journal of virology*, 80(22), 11055-11061.

Honaker J, King G et al.. Amelia II: A Program for Missing Data. *Journal of Statistical Software*, 45, 7, Pp. 1-47.

Katen, S. P., Tan, Z., Chirapu, S. R., Finn, M. G., & Zlotnick, A. (2013). Assembly-directed antivirals differentially bind quasiequivalent pockets to modify hepatitis B virus capsid tertiary and quaternary structure. *Structure*, 21(8), 1406-1416.

King G., Honaker J., Joseph A., et al. Analyzing Incomplete Political Science Data: An Alternative Algorithm for Multiple Imputation. *American Political Science Review*, Vol. 95:49-69.

Attachment 1. Selected Major Protocol Deviations For Analysis Purposes

The major protocol deviations (MPD) that may affect the assessment of efficacy will be finalized prior to the primary analysis database lock. The major deviations that are selected to exclude participants from the PP set are listed below. The flag of Intercurrent Event is added to each deviation for facilitating the implementation of the estimands for the primary endpoint.

Sequence No.	Protocol Deviation Description (DVTERM)	Protocol Deviation Coded Term (DVDECOD)	Exclude from PP	Intercurrent Event
1	Inclusion criterion M03/A02. not met: Subject did not meet the following: o Be HBeAg-negative, o Be on stable HBV treatment, defined as currently receiving NA treatment (ETV, TDF, or TAF) for at least 24 months prior to screening and having been on the same NA treatment regimen (at the same dose) as used in this study (see Section 6.1) for at least 3 months at the time of screening, AND o Have serum HBV DNA <60 IU/mL on 2 sequential measurements at least 6 months apart (one of which is at screening), AND o Have documented ALT values <2.0x ULN on 2 sequential measurements at least 6 months apart (one of which is at screening).	Entered but did not satisfy criteria	Yes	No
2	Inclusion Criterion A05. not met: Participants have HBsAg ≤100 IU/mL at screening.	Entered but did not satisfy criteria	Yes	No
3	Exclusion criterion M01/A01. met: Participants has evidence of hepatitis A virus infection (hepatitis A antibody IgM), hepatitis C virus (HCV) infection (HCV antibody and detectable HCV RNA), hepatitis D virus (HDV) infection (HDV antibody), hepatitis E virus infection (hepatitis E antibody IgM), or HIV-1 or HIV-2 infection (confirmed by antibodies) at screening.	Entered but did not satisfy criteria	Yes	No
4	Exclusion criterion M02. met: Participant at any time point prior to or at the time of screening has: a. Direct bilirubin >1.2xULN (unless there is documentation of a benign cause such as Gilbert's disease), OR b. Prothrombin time >1.3xULN (unless caused by anticoagulation therapy or vitamin K deficiency), OR c. Serum albumin <3.2 g/dL, OR d. History of clinical symptoms of hepatic decompensation (eg, ascites, jaundice, hepatic encephalopathy or coagulopathy, especially if resulting in a Child-Pugh classification B or C at the time clinical symptoms present or at screening).	Entered but did not satisfy criteria	Yes	No
5	Participants with evidence of hepatic decompensation at any time point prior to or at the time of screening: a. Total bilirubin >1.5xULN, b. Direct bilirubin >1.2xULN OR c. Prothrombin time >1.3xULN (unless caused by anticoagulation therapy or vitamin K deficiency), OR d. Serum albumin <3.2 g/dL, OR e. History of clinical symptoms of hepatic decompensation (eg, ascites, jaundice, hepatic encephalopathy or coagulopathy, especially if resulting in a Child-Pugh classification B or C at the time clinical symptoms present or at screening).	Entered but did not satisfy criteria	Yes	No
6	Exclusion criterion M03. met: Participant has a history or evidence of hepatic decompensation ((eg, ascites, jaundice, hepatic encephalopathy or coagulopathy.)	Entered but did not satisfy criteria	Yes	No
7	Exclusion criterion M04. met: Participant has evidence of liver disease of non HBV etiology	Entered but did not satisfy criteria	Yes	No

Sequence No.	Protocol Deviation Description (DVTERM)	Protocol Deviation Coded Term (DVDECOD)	Exclude from PP	Intercurrent Event
8	Subject used disallowed medication at any time prior to screening until end of follow-up: <specify treatment, dose, unit, frequency, reason administered>.	Received a disallowed concomitant treatment	Yes, if classified as MPD (reviewed case by case)	Yes
9	Subject used disallowed medication from 1 week prior to baseline until 12 weeks after EOS intervention: <specify treatment, dose, unit, frequency, reason administered>.	Received a disallowed concomitant treatment	Yes, if classified as MPD (reviewed case by case)	Yes
10	Received wrong treatment of study drug JNJ-6379 for at least 1 week period: was randomized to receive JNJ-6379 but received placebo or vice versa. <specify study drug administration detailed information, such as study drug dose, start date and time, end time etc. >.	Received wrong treatment or incorrect dose	Yes, if classified as MPD (reviewed case by case)	Yes
11	Received wrong treatment of study drug JNJ-3989 for at least 2 or more times: was randomized to receive JNJ 3989 but received placebo or vice versa <specify study drug administration>.	Received wrong treatment or incorrect dose	Yes, if classified as MPD (reviewed case by case)	Yes
12	Subject did not receive dose of study drug JNJ-3989 within window: Within three weeks of the planned administration JNJ-3989 should be administered, If realized later than three weeks the dose should be skipped and administration of the next planned dose as per visit schedule should be awaited. <Specify duration>	Received wrong treatment or incorrect dose	Yes, if classified as MPD (reviewed case by case)	Yes
13	Subject missed more than 5 JNJ-6379/Placebo doses within a four week period.	Received wrong treatment or incorrect dose	Yes, if classified as MPD (reviewed case by case)	Yes
14	Subject missed NA treatment for more than 5 doses within a four week period.	Received wrong treatment or incorrect dose	Yes, if classified as MPD (reviewed case by case)	Yes
15	Subject received expired study medication <JNJ-3989, JNJ-6379, NA or placebo>.	Received wrong treatment or incorrect dose	Yes, if classified as MPD (reviewed case by case)	Yes
16	Subject continue NAs despite no relevant change in participant baseline status with regards to ALT, HBV DNA levels and/or HBeAg status or without any discussion with the sponsor regarding event that could prevent stopping NA	Received wrong treatment	Yes, if classified as MPD (reviewed case by case)	Yes
17	Subject has event of signs of decreasing liver function based on laboratory findings or clinical findings, but did not start NA treatment	Received wrong treatment or incorrect dose	Yes, if classified as MPD (reviewed case by case)	Yes
18	Subject has confirmed HBeAg seroreversion, but did not start NA treatment.	Received wrong treatment or incorrect dose	Yes, if classified as MPD (reviewed case by case)	Yes
19	Subject has a confirmed post-treatment increase in HBV DNA >2,000 IU/mL and ALT >5 x ULN over a period of at least 4 weeks, but did not start NA treatment	Received wrong treatment or incorrect dose	Yes, if classified as MPD (reviewed case by case)	Yes
20	Subject has a confirmed post-treatment increase in HBV DNA >20,000 IU/mL over a period of at least 4 weeks, but did not start NA treatment	Received wrong treatment or incorrect dose	Yes, if classified as MPD (reviewed case by case)	Yes
21	Subject has confirmed signs of hepatic decompensation <specify> but subject continued study treatment	Developed withdrawal criteria but not withdrawn	Yes	Yes
22	The subject has confirmed HBV virological breakthrough but continued study treatment.	Developed withdrawal criteria but not withdrawn	Yes	Yes
23	Accidental unblinding of treatment group of a subject or a blinded staff member prior to planned unblinding at <specify visit>.	Other	Yes, if classified as MPD (reviewed case by case)	No
24	Study <specify the visit which> procedure not done at scheduled Visits.	Other	Yes, if classified as MPD (reviewed case by case)	No
25	Efficacy evaluation not done at Week 72*	Other	Yes, if classified as MPD (reviewed case by case)	No

* The algorithm to determine if a subject has the major protocol deviation "Efficacy evaluation not done at Week 72" will not only check DV.DVCRIT records, but will also check the central lab data. If a subject is continuing in the trial at Week 72, i.e., not withdraw from the study prior to Week 72, but HBsAg assessment results are not available at analysis visit Week 72 based on the central lab data (LB), the subject will be considered as having the major protocol deviation and will be excluded from the PP set.

